Design/Methodology:	We will conduct a stepped wedge hybrid effectiveness-implementation trial. The intervention proposed is a systems intervention. All subjects will be newly diagnosed breast oncology patients at one of the six participating clinical sites. In a stepped wedge design, sites are randomized to the time the site begins to implement the intervention and stratified by size. This will occur over an 18 month period, with a new site initiating the intervention every three months over this period. Historical data from each site serves as the comparison. Thus, 24 months prior to the time when the intervention begins at each site, women who meet the eligibility criteria will be given usual care (control) arm. Newly diagnosed cancer patients at the site after the time allocated to begin the intervention will be in the intervention arm. There will be no crossover.
Total Study Duration:	August 2018- July 2022
Subject Participation Duration:	Varies depending upon each patient's recommended cancer care as directed by their care team. Study participation will not influence the care recommended by the treatment team. Clinical outcomes will be collected from 0 to 24 months from the time of cancer diagnosis.

---

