## 5.1.5 Accrual and Enrollment

As the intervention is a health systems intervention targeting specific vulnerable patients seeking care across each of the participating health systems, TRIP's partner sites have agreed to roll out the intervention as a new navigation standard of care. As such, all patients meeting study enrollment criteria also meet these new navigation standards. Thus, it is expected that all eligible subjects will be enrolled into the study for the purposes of our effectiveness testing. All women will receive usual clinical care as directed by their treatment team. Navigators are employees of the clinical site and typically are part of the care team for these patients. Given this, and the fact that the intervention is low risk and likely to only improve care delivery, the study team will obtain a waiver of informed consent for study subjects, as it is not practical to obtain their consent and their rights and welfare are protected by rigorous confidentiality measures for the Electronic Health Record (EHR) data.

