## 5.1.6 Data Sources/Collection

**(1) The Electronic Health Records (EHR) will serve as the data source for all socio-demographic and clinical covariates, as well as the primary and secondary clinical effectiveness outcomes for historical controls and intervention subjects. At Boston Medical Center the EHR will also be used to source social needs screening data from a parallel instance of Aunt Bertha called THRIVE. The THRIVE SDOH for TRIP patients will be retrieved from BUMC's Clinical Data Warehouse (CDW) and merged with the social needs screening data from the TRIP instance of Aunt Bertha by the TRIP analyst. The clinical and demographic EHR data from the 6 sites will be used in two ways: 1) to create a *potential patient list* to aid Patient Navigators in identifying potentially eligible patients with new breast cancer diagnoses (these data will be kept at the clinical site) and 2) treatment data needed for TRIP analysis (i.e., Chemotherapy regimens)**

Treatment variables will be *manually abstracted* for both historical controls and enrolled intervention subjects. Abstraction into a HIPAA compliant REDCap form will be completed by trained study personnel 16-18 months after diagnosis to ensure complete treatment information is documented through the 12 months following diagnosis. The electronic health records will also be used to obtain patient contact information (mailing address and phone number) for patient interviews assessing patient acceptability of the intervention.

- (2) **The REDCap registry and SDOH screening platforms (Aunt Bertha, THRIVE, QuickBase)** are the main sources of implementation (Fidelity) data. Each will provide measures of fidelity to the intervention protocol. Navigators utilize these systems to track and monitor their activities related to individual patients. Monthly aggregate reports will be generated for each navigator, reviewed by the study team and used for performance improvement throughout the study. Fidelity metrics include categorical assessments of navigator use of these tools, and will be linked to outcomes. The REDCap registry and SDOH screening platforms will also be used to identify navigated patients for patient acceptability interviews. Only patients who have been contacted by a TRIP patient navigator and screened for social determinants of health will be contacted for participation in interviews.

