# **7 Study Subject Selection**

## **7.1 Subject Inclusion Criteria**

In order to be eligible to participate in this study, an individual must meet all of the following criteria:

Eligibility criteria: All women with breast cancer diagnosed during the study period will be eligible for inclusion if they meet three study criteria:

1. are an adult female 18 years of age or older;
2. reside within a 35 mile radius of Boston;
3. have any of the following risk factors for delays in care:
  - a. Black and/or Hispanic race/ethnicity
  - b. do not speak English as their primary language and/or
  - c. have only public insurance or are uninsured at the time of diagnosis.

Women who do not meet all three criteria will be excluded from the study. In some cases it is possible, due to the scope of the patient navigator's responsibilities that patients who are ineligible will be entered into the Registry. As the registry is HIPAA compliant and these individuals will be excluded from compiled data sets, the study team does not perceive this to be a major risk.

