### 9.1 Patient Navigation services

Patient Navigation services at each site will follow standard operating procedures that are guided by the Principles of Care Management in collaboration with a network of navigators across the six health systems. In order to have the desired effect on treatment delays, we aim to disseminate the following 'best practices' of patient navigation across each hospital setting:

- Patient navigation is a process not a person: no one person can navigate alone, there is potential role for lay, nurse and SW in the process of navigating a patient through their treatment; multiple 'navigators' may participate across the treatment trajectory; the optimal structure will be specific to the needs and resources at each hospital
- The patient navigation process should begin within 7 days of diagnosis and continue until treatment recommendations have been completed
- Patient navigation services include the following 4 procedures:
  1. **Identify those in need of navigation:** TRIP eligibility criteria have been chosen to identify those most at risk for delays in care (as defined by MA Cancer Registry Data). Navigators will identify eligible patients in partnership with the oncology care team by any of the following existing processes: reviewing automated potential patient lists generated from upcoming oncology schedules, reviewing pathology reports, attending tumor board meetings, manually reviewing physician schedules, or direct referrals from providers. Once identified as eligible for navigation services, they will obtain permission to contact the patient from the care team and create a Patient Profile in the REDCap Registry based on available information from the EHR.

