### **9.3.3 Data elements**

The data elements included in the registry are the minimum information needed by navigators to actively manage and support their patients, assist them in keeping clinical appointments, and address the social determinants that often result in patients delaying or falling out of clinical care. Therefore the registry will not have extensive clinical information about the type of cancer, specific types of treatment, medications, comorbidities or complications of care. Additionally, only MRN, patient first and last name, date of birth, phone number, and study eligibility criteria are required, all other fields are optional, and navigators will be the only individuals entering data in these fields. The registry will include the following categories of data elements:

1. Patient demographics – Sufficient demographic information to uniquely identify women in the data base, including first and last name, date of birth and medical record number from each hospital system where a patient receives care. Preferred language, race/ ethnicity and gender identification fields will be available to assist navigators identify patients and their needs. A free text field will allow navigators to input specific biographical data which will help in the care of the patient (such as background, family structure, hobbies).
2. Minimal clinical information necessary for navigators to conduct their work. This will include stage of diagnosis and date of diagnosis, as this information will help navigators focus on meeting clinical benchmarks including first surgery within 45 days and first treatment within 60 days. It will also include insurance and a free text field to document any insurance restrictions/ need for prior authorizations, etc.
3. Patient contact information – detailed information to assist navigators in communicating with patients, including address, phone numbers, email, and social media as appropriate

4. Family/ secondary contact information – detailed information on 2 – 3 individuals the navigator can contact in event of emergency or patient not keeping appointments, including phone, email.
5. Patient navigator information– who is the navigator for the patient, and contact information for navigator and his/her supervisor
6. Referral source – how patient was referred to navigator and specific concerns that prompted referral

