#### **9.3.4 Patient Identification**

Navigators will identify patients in 2 ways: 1) using their standard methods as part of their clinical workflow. The majority of patients will be identified via physician or social worker referral at the clinical site of origin, or through discussion of the case in the Breast Cancer tumor board or case conference. 2) using a potential patient list provided by their site's IT/Research Administration to review patients that match eligibility criteria prior to an upcoming scheduled oncology appointment.

As part of the TRIP intervention, patient navigators at each of the 6 clinical sites are responsible for identifying eligible patients based on the aforementioned eligibility criteria. In order to facilitate effective identification of eligible patients as part of each navigator's workflow, the TRIP

team is collaborating with Information Technology personnel at each clinical site to produce a potential patient report. At each individual site, these reports will be generated weekly from electronic medical records and produce a list of patients who meet the following criteria:

1. A scheduled visit for a diagnosis of breast cancer in the next one to two weeks
2. A ZIP code within a 35 mile radius of Boston
3. Other key eligibility criteria (non-white, non-English speaking, and/or uninsured/public insurance)

The PHI data included in these reports are patient name, MRN, appointment type, provider, race/ethnicity, primary language, ZIP code, and insurance (if available). These reports are unique to each site and are accessible locally via secure folder or encrypted email by a patient navigator and in some cases, study team personnel at their site.

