#### **10.1.5 Data Source: Electronic Health Records**

Treatment data elements will be manually abstracted for both historical control and intervention subjects from **Electronic Health Records (EHR)** at each site. Abstraction from the EHR will be conducted by a trained Research Assistant employed by that site and overseen by the site PI. Data elements from EHR abstraction will be uploaded or entered directly into the TRIP REDCap abstraction project. For more information, see *Figure 1 Table 1*.

**Intervention patients:** Potential Patient Lists will be generated locally at each participating institution to aid Patient Navigators in identifying potentially eligible patients with new breast cancer diagnoses. Every week, Patient Navigators will receive a list of patients who meet TRIP eligibility criteria and have an upcoming appointment for the following week. These lists will be generated by the EHR via a script developed by each site's IT department or research administration group and uploaded to a secure folder on the Patient Navigator's local drive or sent locally through secure email.

**Historical Controls:** Historical controls will be identified by working with each site's tumor registrar to generate a list of all breast cancer patients during the historical time period. These data will be securely stored locally at each site, and transmitted to the TRIP study team at BMC via secure Box.com folder, SFTP, or secure email. The data will then be saved to the secure tripdata\$ folder. These data will be reviewed by the TRIP data analyst to ensure completeness and correct formatting of files, and to exclude all ineligible patients according to TRIP eligibility requirements. Then the TRIP data analyst will upload the eligible patients' data to a secure REDCap project for chart abstraction. This REDCap project will be used to store clinical data manually abstracted from each EHR, and entered by the site's Research Assistant.

Historical control datasets will include the following variables requested from each site:

- a. First Name
- b. Last Name
- c. MRN
- d. Sex
- e. Race/ethnicity
- f. Date of diagnosis
- g. Date of birth

- h. ZIP code at diagnosis
- i. Primary institution
- j. Primary payer at diagnosis
- k. Date of last contact or death

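### Controls come from a tumor-registrar list and intervention women from navigator identification, and nothing checks that the intervention list is complete, so the comparison is open to selection bias

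*Combined protocol and SAP*

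**What the plan says.** **Controls.** Section 10.1.5: "Historical controls will be identified by working with each site's tumor registrar to generate a list of all breast cancer patients" in the historical period. The study's data analyst reviews the files for completeness, removes ineligible women and uploads the rest for chart abstraction. Table 1 (with Figure 1) likewise limits the registrar lists to the historical control period.

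**Intervention women.** Section 9.1 has navigators find eligible patients by several routes, including "reviewing automated potential patient lists generated from upcoming oncology schedules, reviewing pathology reports, attending tumor board meetings". Section 9.3.4 says: "The majority of patients will be identified via physician or social worker referral at the clinical site of origin", or through case discussion. A weekly EHR list supports the navigators, but it shows only patients with a scheduled visit in the next one to two weeks. The navigator creates the REDCap record, and its number later becomes the identifier for the coded analysis data (section 10.3.5). Section 5.1.6 has treatment variables abstracted "for both historical controls and enrolled intervention subjects".

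**What is intended.** Section 2: "Newly diagnosed cancer patients at the site after the time allocated to begin the intervention will be in the intervention arm". Section 5.1.5: "it is expected that all eligible subjects will be enrolled into the study". Section 12.3 commits to intent-to-treat.

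**Eligibility fields.** Criterion 3a in section 7.1 is "Black and/or Hispanic race/ethnicity"; the weekly list in section 9.3.4 screens on non-white. The control variable list in section 10.1.5 has no language field, whereas Table 1 includes preferred language.

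**The concern.** Before go-live, a woman is counted because the registrar recorded her cancer. After go-live, she is counted because a navigator found and entered her. Finding her is itself the first of the four navigation procedures in section 9.1, so membership of the intervention group depends partly on delivery of the intervention. Controls passed through no such filter.

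This matters only if capture is incomplete and related to timeliness, and either direction is plausible. If women who are slow to reach oncology are also the ones missed, the intervention group looks faster than it is. If navigators preferentially receive women at risk of delay, it looks slower; section 9.3.3 records "specific concerns that prompted referral", so referral can be driven by worry about a patient. If capture is complete, or if missed women are as timely as those found, there is no bias. As long as no registrar list is drawn for the intervention period, the data cannot show which case applies.

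**Working it through.** **Step 1: is there any check that would find a missed woman?**

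- Section 10.2.3: quarterly enrollment is compared with goals, and eligibility of those enrolled is checked. This could show a shortfall in numbers but not who is missing.
- Section 9.3.5: weekly reports cover women already entered.
- Section 10.6: the 15% sample tests the accuracy of abstracted data.
- Section 10.1.5: the state cancer registry match covers controls only, to detect transfers of care.
- Section 7.1: ineligible registry entries are removed later. This corrects over-inclusion, not omission.

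None compares the intervention list with an independent list of cases for the same period.

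**Step 2: inputs.** From section 12.2: 70% treated by time t under usual care, 81% under intervention (a difference of 11 points), design effect 2.29, two-sided alpha 0.05. From section 5.1.4 and Table 6: 633 controls and 667 intervention women. The plan's own minimum reproduces: 2 × 220 × 2.29 = 1,007.6, rounded up to 1,008. Two quantities are not in the documents and are assumed over a range: m, the share of eligible intervention women missed (5% to 30%), and p, the timely proportion among those missed (50% to 90%).

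**Step 3: false difference with no true effect.** If 70% of all eligible women are timely in both periods, the proportion among those captured is (0.70 − m·p)/(1 − m). For example, m = 0.20 and p = 0.50 gives (0.70 − 0.10)/0.80 = 0.750, or +5.0 points. The table shows the apparent difference in percentage points.

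| m | p = 50% | p = 60% | p = 70% | p = 80% | p = 90% |
|---|---|---|---|---|---|
| 5% | +1.1 | +0.5 | 0 | −0.5 | −1.1 |
| 10% | +2.2 | +1.1 | 0 | −1.1 | −2.2 |
| 15% | +3.5 | +1.8 | 0 | −1.8 | −3.5 |
| 20% | +5.0 | +2.5 | 0 | −2.5 | −5.0 |
| 30% | +8.6 | +4.3 | 0 | −4.3 | −8.6 |

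**Step 4: effect on the test.** The standard error with no true effect, using crude proportions, is √[2.29 × 0.7 × 0.3 × (1/633 + 1/667)] = 0.0385, about 3.8 points. With absolute bias b, the chance of a significant result is 1 − Φ(1.96 − b/0.0385) + Φ(−1.96 − b/0.0385).

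| Absolute bias (points) | Chance of a significant result |
|---|---|
| 0 | 5.0% |
| 0.5 | 5.2% |
| 1.1 | 6% |
| 1.8 | 7.4% |
| 2.2 | 8.9% |
| 2.5 | 10% |
| 3.5 | 15% |
| 4.3 | 20% |
| 5.0 | 26% |
| 8.6 | 60% |

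**Step 5: extra charts if the gap is closed.** With 667 enrolled, the number missed is 667·m/(1 − m): 35 at 5%, 74 at 10%, 118 at 15%, 167 at 20% and 286 at 30%.

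**The case against.** Five points can be made for the plan.

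- **Capture may be nearly complete.** Pathology review, tumor board, schedules and weekly EHR lists together form a wide net. That may be so, but nothing verifies it; if it is so, the fix needs no extra charts.
- **A large gap would be noticed.** Missing 15–30% would appear as a shortfall in quarterly monitoring. This stands in part: it would prompt questions if the projection is accurate, but it would not identify the missing women, and a 5–10% gap could pass unseen.
- **667 can be read as the number eligible, not the number captured.** Section 5.1.4 bases it on state cancer registry statistics. Then 667·m women are missed: 33–67 at 5–10% and 100–200 at 15–30%. At 30% missed the captured group is 467, the standard error is about 4.2 points and the worst-case chance is about 53% instead of 60%. Table 6 is titled as a recruitment projection, so either reading is fair and the conclusion is unchanged.
- **The model adjusts for race, language and insurance.** Selection acting through those variables would be partly handled, and the figures above are unadjusted. Adjustment cannot restore absent women whose timeliness differs for other reasons.
- **The field mismatches are minor.** This is fair. Navigators apply the formal criteria, and Table 1 supplies language for controls. They are reasons for one common filter, not evidence of missed women.

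**Conclusion.** The concern holds. The two groups are ascertained by different routes, and no step secures the all-eligible intervention group that sections 2 and 5.1.5 intend and that intent-to-treat requires. That rests on the text and is firm.

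The size of any bias is not known. It is zero under complete capture or equal timeliness. Under the assumed ranges it is small if 5–10% of women are missed, at most 2.2 points and a 9% chance of a significant result. If 15–30% are missed it could reach 8.6 points in either direction, most of the planned 11-point effect. These figures assume no true effect, crude proportions and the plan's design effect of 2.29. The matter should be fixed because it bears on the primary comparison and the remedy uses a process already in place.

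**What to change.** - Define the intervention-period analysis set with the same tumor-registrar query and central eligibility filter used for controls, covering all diagnoses after each site's go-live and still excluding washout.
- Assign group by site and diagnosis date, as section 2 already intends.
- Abstract outcomes for every eligible woman, whether or not a navigator entered her in REDCap.
- Report capture by site: navigator-entered eligible women divided by registrar-listed eligible women. Use the navigator-enrolled subset for fidelity only.
- Apply identical eligibility fields in both periods: add primary language to the control list in section 10.1.5, and replace non-white in section 9.3.4 with criterion 3a of section 7.1.

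**Cost.** One repeat registrar query per site, protocol wording, and abstraction of any missed women. On top of 667 this is about 35–74 charts if 5–10% were missed, 118–286 (18–43%) if 15–30% were missed, and none if capture is complete. Because abstraction is scheduled 16–18 months after diagnosis (section 5.1.6), a retrospective query fits the sequence. Extra charts for the latest diagnoses would fall close to the July 2022 study end and should be planned for.

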## **9.3 Use of Shared Registry**

### **9.3.1 REDCap**

A shared TRIP registry was developed using REDCap (Research Electronic Data Capture), a HIPAA compliant, secure web-based application for building and managing online surveys and databases. The purpose of the registry is to improve the workflow processes of the patient navigators as part of their routine clinical duties and as part of new standard of care. The registry will also permit close coordination of clinical care across hospitals for the estimated 20% of patients who receive their cancer care at more than one institution, or switch from one institution to another during their care.

The REDCap registry developed for TRIP resides on BMC HIPAA compliant server. Access to the TRIP shared registry will be based on permissions granted by username and password

which will be managed by the Boston Medical Center Office of Information Technology. Only authorized study members will be able to enter or view data.

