In order to identify which historical control patients transferred their care to multiple institutions, the TRIP team will cross-reference historical control cases with the Massachusetts Cancer Registry (MCR) at the Massachusetts Department of Public Health (MADPH). The TRIP team will transmit the following data via SFTP to MCR, which will perform a matching query to report which patients have received care at more than one institution:

- a. First Name
- b. Last Name
- c. MRN
- d. Date of diagnosis
- e. Date of birth
- f. Reporting institution

The electronic health records will also serve as a data source for patient interviews. The site's RA will query the electronic health records directly through Epic or other electronic medical record system at a site for the following data:

- a. First name
- b. Last name
- c. Mailing address
- d. Phone number

These data will be securely stored locally at each site, and transmitted to the TRIP study team at BMC via secure Box.com folder, SFTP, or secure email.

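### Care at more than one institution is identified by a state cancer registry match in controls only, and the plan does not say how this, or the navigator registry used for intervention women, directs abstraction of first-treatment dates

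*Combined protocol and SAP*

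**What the plan says.** **Controls.** Section 10.1.5 has tumor registrars list the historical controls. It then adds a match to the state cancer registry, introduced by "In order to identify which historical control patients transferred their care to multiple institutions". Six fields are sent: first name, last name, MRN, date of diagnosis, date of birth and reporting institution. The query is to "report which patients have received care at more than one institution". No treatment dates are listed among what comes back, and no use of the result is stated.

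**Intervention women.** No section describes this match for them. Section 9.3.3 describes a shared registry that holds a record number from each hospital system a woman uses. Section 9.3.6 adds a messenger for second opinions, split care and transfers. Beyond a short required list (MRN, name, birth date, phone number, eligibility criteria), "all other fields are optional, and navigators will be the only individuals entering data in these fields". The overview of patient identifying elements in Section 10.1 gives the registry's purpose as implementation data.

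**Outcome dates, both arms.** Section 10.1.5 states: "Treatment data elements will be manually abstracted for both historical control and intervention subjects from" the electronic health record at each site, by an assistant employed there. Section 5.1.6 names the record as the source for covariates "as well as the primary and secondary clinical effectiveness outcomes for historical controls and intervention subjects". It sets one abstraction window, "16-18 months after diagnosis to ensure complete treatment information is documented through the 12 months following diagnosis".

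**How common it is.** Section 9.3.1 refers to the "estimated 20% of patients who receive their cancer care at more than one institution", or who switch institution during care.

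**The concern.** The primary outcome in Section 4.2.1 runs from diagnosis to the earliest of surgery, radiation, chemotherapy or hormone therapy. The timely-initiation proportion analysed in Section 12.3 depends on the same date. When a woman is diagnosed at one hospital and first treated at another, an abstractor working in the first hospital's chart may need to be told to look elsewhere.

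The prompt to look differs by arm. For controls it is external and systematic. For intervention women it comes largely from the intervention's own registry, so it depends partly on navigator contact and on what the navigator recorded. If a missed outside treatment is recorded as a later treatment or as none, and this happens more often in one arm, part of the estimated effect is an artefact of ascertainment. A larger sample would not remove it.

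**Working it through.** **1. The plan's sample-size figure.** Section 12.2 gives 220 per group and a design effect of 2.29: 2 × 220 × 2.29 = 1,007.6, rounded up to the stated 1,008. Nothing below changes that figure; the 2.29 is used only to put bias on the scale of the planned precision.

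**2. Women exposed to the issue.** Multi-institution share 20% (Section 9.3.1); planned numbers 633 and 667 (Section 5.1.4).
- Controls: 0.20 × 633 = 126.6, about 127.
- Intervention: 0.20 × 667 = 133.4, about 133.

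**3. Bias formula.** Let f be the share of multi-institution women in an arm whose first treatment was elsewhere and was missed. Assume a missed treatment counts as not timely (the plan states no coding rule). The observed timely proportion is then p × (1 − 0.20 f), with p = 81% for intervention and 70% for controls (Section 12.2). The documents do not give f; 0.10 to 0.50 is an assumed range.

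**4. Misses in the intervention arm only.** The loss is 0.81 × 0.20 × f.
- f = 0.10: 2% of 667 = 13 women; loss 1.6 points; 11.0 becomes 9.4.
- f = 0.25: 5% = 33 women; loss 4.05 points; 11.0 becomes 6.95.
- f = 0.50: 10% = 67 women; loss 8.1 points; 11.0 becomes 2.9.

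With effective sizes 633/2.29 = 276 and 667/2.29 = 291, a two-sided 5% comparison of 70% with 81% has about 86% power. In the three cases it falls to about 73%, 47% and 12%.

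**5. Misses in controls only, no true effect (70% in both arms).** The false difference is 0.70 × 0.20 × f: 1.4, 3.5 and 7.0 points. At the same effective sizes, the chance of rejecting is about 7%, 15% and 42%, against a nominal 5%.

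**6. Equal misses in both arms.** The difference is multiplied by (1 − 0.20 f). At f = 0.50, 11.0 becomes 11.0 × 0.90 = 9.9. Equal misses shrink a true difference slightly and cannot create a false one. The serious bias comes from the difference in f between arms.

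**7. How far steps 4 and 5 overstate.** They are one-sided extremes: all misses fall in one arm. Reading f as a pure miss rate also assumes that every multi-institution woman began treatment elsewhere. If half did (an assumption), 1.6 to 8.1 points halves to 0.8 to 4.05.

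**The case against.** A reader might infer that first-treatment dates are ascertained by different methods in the two arms. The documents do not support that. Source, staff and window are the same in both arms (Sections 5.1.6, 10.1.5 and 10.3.3). The match is described only as showing who had care at more than one institution, and it may serve merely to describe transfers.

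A reader might also infer that outside care in the intervention arm is known only through optional navigator fields. That is too strong. MRN is a required field and the registry is meant to hold one from each hospital system, although the plan does not say every outside number must be entered. Each site also produces weekly lists from its electronic records, appointments can be tracked by location, navigators can message each other across sites, and the chart itself may record outside treatment. Controls had no shared registry, so the match may fill a gap for them rather than give them better capture. The direction is unknown.

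The size can be challenged too. The 20% covers any multi-institution care. The similar estimate in Section 9.3.6 includes second opinions and later treatments split between hospitals, so many of these women will have started treatment at the first hospital. Section 5.1.3 says the six systems care for over 90% of the target women.

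All of this stands and limits the claim. It does not show that the two routes are equivalent, and it does not supply the missing rule on how either one feeds abstraction.

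**Conclusion.** The asymmetry is in the text: a state registry match for controls, and a navigator-entered six-site registry plus ordinary chart review for intervention women. The plan does not say how either directs abstraction of first-treatment dates. If the flag is used to search for outside treatment, differential capture is possible and the primary comparison could be biased in either direction. Bias in the primary outcome is not demonstrated.

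About 127 controls and 133 intervention women are potentially affected. The loss of 1.6 to 8.1 points against the 11-point target is an upper-end illustration. It assumes that all multi-institution women started treatment elsewhere, that 10% to 50% of these starts were missed in the intervention arm, that none were missed in controls, and that a missed start counts as not timely. None of these assumptions comes from the documents. The change is worth making because the query already exists for one arm and the opportunity to extend it is limited in time.

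**What to change.** 1. Send intervention women through the same state registry match with the same six fields. Name, MRN and birth date are required registry fields; diagnosis date and institution are in the chart abstraction. Do this before the master identifier file is destroyed at study completion (Section 10.3.4 gives June 2022).
2. State in Section 10.1.5 how a flag is used, identically in both arms: a flagged woman has her first-treatment date abstracted from the other participating sites where she received care.
3. Where the match shows outside care only at a non-participating hospital, apply one written rule to both arms. Abstraction staff are employed only at the six sites, so the plan has no means of abstracting charts elsewhere.
4. Where the registry is incomplete for the latest diagnoses, add a sensitivity analysis of the primary outcome restricted to diagnosis years that could be matched.
5. Report by arm the number flagged and the number whose first-treatment date changed after outside abstraction. This replaces the assumed range for f with data.

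The cost is one more secure file to an existing query, an IRB amendment, some extra chart abstraction at participating sites, and registry lag for the latest diagnoses. No sample-size figure changes.
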